10.6 Required Routine Reporting

10.61 **Baseline and Adverse Events Evaluations**

Pretreatment symptoms/conditions to be graded at baseline and adverse events to be graded at each evaluation.

Grading is per CTCAE v4.0 **unless** alternate grading is indicated in the table below:

CTCAE System/Organ/Class (SOC)	Adverse event/Symptoms	Baseline	Each evaluation
Immune system disorders	Allergic reaction	X	X
Investigations	Alanine aminotransferase increased	X	X
	Aspartate aminotransferase increased	X	X
	Alkaline phosphatase	X	X
	Weight gain		X

10.62 All other AEs

Submit via appropriate MCCC Case Report Forms (i.e., paper or electronic, as applicable) the following AEs experienced by a patient and not specified in Section 10.6:

10.621 Grade 1 and 2 AEs deemed *possibly, probably, or definitely* related to the study treatment or procedure.

10.622 Grade 3 and 4 AEs regardless of attribution to the study treatment or procedure.

10.623 Grade 5 AEs (Deaths)

10.6231 Any death within 30 days of the patient's last study treatment or procedure regardless of attribution to the study treatment or procedure.

10.6232 Any death more than 30 days after the patient's last study treatment or procedure that is felt to be at least possibly treatment related must also be submitted as a Grade 5 AE, with a CTCAE type and attribution assigned.

#### 10.7 Late Occurring Adverse Events

Refer to the instructions in the Forms Packet (or electronic data entry screens, as applicable) regarding the submission of late occurring AEs following completion of the Active Monitoring Phase (i.e., compliance with Test Schedule in Section 4.0).

### 11.0 Measurement of Effect

Measurement of effect will be determined based on whether a patient developed a healthcare provider-witnessed hypersensitivity reaction or not per CTCAE v 4.03

Patients who stop carboplatin or oxaliplatin for any reason other than a hypersensitivity reaction will be censored on the date of their last study infusion.

**12.0 Descriptive Factors**

- 12.1 Cancer type: ovarian cancer vs endometrial cancer vs colon cancer vs other cancer
- 12.2 Has the patient had an interval of 12 months or longer at any time between carboplatin/oxaliplatin treatments? yes versus no

**13.0 Treatment/Follow-up Decision at Evaluation of Patient****13.1 Ineligible**

A patient is deemed *ineligible* if after registration, it is determined that at the time of registration, the patient did not satisfy each and every eligibility criteria for study entry.

- If the patient received treatment, all data up until the point of confirmation of ineligibility must be submitted.
- If the patient never received treatment, on-study material must be submitted.

**13.2 Major violation**

A patient is deemed a *major violation*, if protocol requirements regarding treatment in the initial therapy are severely violated that evaluability for primary end point is questionable. All data up until the point of confirmation of a major violation must be submitted.

**13.3 Cancel**

A patient is deemed a *cancel* if he/she is removed from the study for any reason before any study treatment is given. If the patient never received treatment, on-study material must be submitted.

**13.4 Off study**

Patients will go off study for the following reasons:

- Investigator discretion
- Treatment related adverse event (immune reaction or unexpected CTCAE  $\geq$ Grade 3 event)
- Switching to different chemotherapy
- Refusal of further treatment on this study
- Death

Patients will go off study and no further follow-up is required.

## 14.0 Body Fluid Biospecimens

### 14.1 Summary Table of Research Blood and Body Fluid Specimens to be Collected for this Protocol\*

Correlative Study (Section for more information)	Mandatory or Optional	Blood or Body Fluid being Collected	Type of Collection Tube (color of tube top)	Volume to collect per tube (# of tubes to be collected)	24 hours prior to lipid/placebo infusion	Within 2 hours following lipid infusion	24 hours after chemo infusion	Process at site? (Yes or No)	Temperature Conditions for Storage /Shipping
Blood  (Section 14.4)	Mandatory	Whole Blood	Red top	10 mL	X	X	X	Yes	-80 degrees Centigrade
Urine  (Section 14.4)	Mandatory	24 hour urine		10 mL	X		X	Yes	-80 degrees Centigrade

1. Blood draw timed with dropping off of the 24 hour urine collection.

2. The patient may pick up kit prior to starting the infusion but must wait to start collection until infusion has been completed.

### 14.2 Collection and Processing

14.21 Blood samples will be centrifuged. Serum will be removed and stored at -80 degrees Centigrade for assay completion at a later date.

14.22 24 hour urine samples will be have a small aliquot of 10 cc removed, frozen at -80 degrees Centigrade and stored for assay completion at a later date.

### 14.3 Shipping and Handling

14.31 Kits will not be used.

14.32 After collection, blood and urine will be stored for future assays as noted below.

### 14.4 Background and Methodology

14.41 Serum tryptase will be measured with a quantitative enzyme-linked immunosorbent assay [59-61]. Based on previous data from our group, we anticipate a level of 11 ng/mL or greater at time point #1 in patients at risk for a hypersensitivity reaction (we hypothesize we will subsequently observe this reaction in the placebo group, although we will be agnostic to biomarker results at the time of carboplatin infusion) with a drop to below this level with lipids and no change with placebo at time point #2, and with a sustained drop with lipids and no change with placebo at time point #3 [59-61].

14.42 11-beta PGF2a, the most abundant prostaglandin D2 metabolite, will be assessed with a 24 hour urine collection with an immunoassay kit at time points #1 and #3. We anticipate a level of >1000 ng/24 hours or greater in patients about to sustain a carboplatin reaction at time point #1 (we hypothesize we will subsequently observe this reaction in the placebo group, although we will be agnostic to real time biomarker results during the carboplatin infusion) with a drop to below this level with lipids and no change with placebo at time point #3 [59-61].

- 14.43 Leukotriene E4 will be measured in urine with liquid chromatography-tandem mass spectrometry. We anticipate a concentration of >104 pg/mg or greater at time at time point #1 in patients about to sustain a carboplatin reaction (we hypothesize we will subsequently observe this reaction in the placebo group, although we will again be agnostic to real time biomarker results) with a drop with lipids and no change with placebo at time point #3 [59-61].
- 14.44 N-methylhistamine will be also assessed in urine. We anticipate a level of >200 mcg/g or greater at time point #1 in patients about to sustain a carboplatin reaction (we hypothesize we will subsequently observe this reaction in the placebo group, although we will again be agnostic to biomarker results) with a drop with lipids and no change with placebo at time point #3 [59-61].

## 15.0 Drug Information

### 15.1 Intravenous Fat Emulsion 20% (Intralipid® 20%)

#### 15.11 Background:

Intravenous Fat Emulsion 20% is a sterile, non-pyrogenic fat emulsion prepared for intravenous administration as a source of calories and essential fatty acids. We will purchase this product and will test it because 1) most published reports on the resuscitative role of lipids for drug overdoses used the same or similar formulations and 2) a safety record is well-established.

#### 15.12 Formulation:

The lipid emulsion used in this study will consist of 100 mL of Intralipid® 20%, which contains 20% soybean oil, 1.2% egg yolk phospholipids, 2.25% glycerin, and water for injection. The major fatty acid components include linoleic acid (44-62%), oleic (19-30%), palmitic (7-14%), linolenic (4-11%), and stearic (1.405.5%). Intralipid 20% is available in 100 mL, 250 mL, and 500 mL fill sizes. The Intralipid 20% utilized in this study will be supplied in a 100 mL bags.

#### 15.13 Preparation and storage:

Administer by IV infusion only via a separate peripheral line. Use a Baxter 1.2 micron in-line filter set (set #2H8486) which is a non-DEHP administration set.

**Note: Filters of less than 1.2 micron pore size must not be used. Also, conventional administration sets contain polyvinyl chloride (PVC) components that have DEHP (di(2-ethylhexyl) phthalate) as a plasticizer. Fat-containing fluids such as Intralipid® 20% extract DEHP from these PVC components.**

Pharmacy will mask the infusion by placing an amber bag over the IV bag and set.

Intralipid® 20% should not be stored above 25°C (77°F). Do not freeze Intralipid® 20%. If accidentally frozen, discard the bag. admixture instructions, light sensitivity, temperature for storage, product specific information.

#### 15.14 Administration:

Initiate infusions of 20% emulsions at 0.5 mL/minute for 15 to 30 minutes; if no untoward effects occur, the infusion rate may be increased to 1 mL/minute.

**15.15 Pharmacokinetic information:**

Metabolism: Fatty acids, phospholipids, and glycerol are metabolized by cells to adenosine triphosphate (ATP), carbon dioxide, and water

Half-life elimination: 0.5 to 1 hour

Excretion: Biliary (phospholipids)

**15.16 Potential Drug Interactions:**

Premedications and chemotherapy agents may be incompatible with fat emulsions. Therefore, a separate peripheral site should be used to infuse the fat emulsion.

**15.17 Known potential toxicities:****Adverse Reactions Significant 1% to 10%:**

Endocrine & metabolic: Hyperglycemia, hyperlipidemia

Gastrointestinal: Nausea, vomiting

Hematologic & oncologic: Hypoproteinemia

Hepatic: Abnormal hepatic function tests

**Frequency not defined:**

Gastrointestinal: Gallbladder disease

Genitourinary: Urinary tract infection

Hepatic: Hepatic abnormality

Infection: Septicemia

Miscellaneous: Fever

<1% (Limited to important or life-threatening): Decreased INR, diarrhea, hypersensitivity reaction (including rash and dyspnea)

Consult the package insert for the most current and complete information.

**15.18 Drug procurement:** This product is manufactured by Fresenius Kabi, Uppsala, Sweden for Baxter Healthcare Corporation, Deerfield, IL.

Drug will be purchased through our usual pharmacy purchasing channels and received at the following shipping addresses:

Mayo Clinic Rochester  
Attn: Cancer Center Research Pharmacist  

**15.19 Nursing Guidelines:**

15.191 Fat emulsion 20% should be delivered via a separate peripheral IV infusion line, with a 1.2 micron in-line-filter set.

15.192 Infusion should start at 0.5 ml/minute if no problems after 15-30 minutes infusion may be increased to 1 ml/minute. Consult the protocol for specific administration rates.

15.193 Fat emulsion 20% can cause hyperglycemia and hyperlipidemia. Monitor labs as outlined in the protocol

## 16.0 Statistical Considerations and Methodology

### 16.1 Endpoints

#### 16.11 Primary Endpoint:

The primary endpoint of this pilot study is **time-to-carboplatin or oxaliplatin acute hypersensitivity reaction** of any grade.

#### 16.12 Translational Endpoint:

We will measure whether lipid infusions modulate a well-established panel of mediators of hypersensitivity reactions that appear to predict reactions.

### 16.2 Study Design

This is a prospective randomized study to explore whether the infusion of a lipid emulsion (versus placebo) prior to carboplatin or oxaliplatin in high risk patients leads to a decrease in incidence of hypersensitivity reactions. Patients will be randomized in a 1:1 ratio to receive a lipid emulsion versus placebo.

### 16.3 Analysis Plan

16.31 Primary endpoint: The primary endpoint is the time to healthcare provider reported hypersensitivity reactions from either carboplatin or oxaliplatin. Kaplan Meier curves will be constructed and a log-rank test will be used to compare time-to-hypersensitivity reaction between treatment arms. Data will be censored based on last infusion with no hypersensitivity reaction with a maximum study treatment duration of 2 years per patient.

16.32 Translational Endpoint: Mediators of hypersensitivity reactions will be assessed in an exploratory fashion to see if they appear to predict hypersensitivity reactions. Due to the nature of this pilot study, results will be summarized and tabulated. Graphics will be used as appropriate, and any testing will be hypothesis generating.

### 16.4 Sample size

Our target sample size is 40 patients (20/arm). If the true hazard ratio is 3.8 (with a median time to a reaction of approximately 2 months, based on our preliminary data and Table 1 data and based on our inclusion criterion that a patient must be starting the 7th cycle of chemotherapy), 20 patients total (10/arm) provides 80% power to detect a prolongation of time-to-hypersensitivity reaction with lipids versus placebo with a 1-sided 5% significance level. Because patients will be censored upon stopping carboplatin or oxaliplatin for a reason other than a hypersensitivity reaction (per section 11.0), we conservatively anticipate high rates of censoring and therefore plan to accrue an extra 20 patients to reach our target sample size of 40 (20 per arm). A log-rank test will be used to compare time-to-carboplatin reactions between arms; a p-value of < 0.05 will be considered statistically significant.

### 16.5 Accrual and Duration of Study

We plan to accrue 40 patients (20 per arm) to this trial to ensure we have 20 (10/arm) evaluable patients. We estimate an accrual rate of 2 patients per month so that we expect

to complete accrual within 2 years. With an expected total time of treatment of 4 months, the expected total duration of the study is slightly over 2 years.

#### 16.6 Missing Data

Missing data are expected to be low in this prospective study primarily because the occurrence of a hypersensitivity reaction will be well-documented in a real-time manner based on the medical necessity. Patients will not be replaced. Nonetheless, we will record and summarize the missing data and look for patterns. In the event, we were to identify patterns, we will decide on the appropriate strategies to account for missing data in our analyses plans. For now, we anticipate that we will rely heavily on censoring; we have inflated our sample size based on anticipated high rates of censoring.

#### 16.7 Data and Safety Monitoring

The study chair(s) and the study statistician will review the study at least twice a year to identify accrual, adverse event, and any endpoint problems that might be developing. The Mayo Clinic Cancer Center (MCCC) Data Safety Monitoring Board (DSMB) is responsible for reviewing accrual and safety data for this trial at least twice a year, based on reports provided by the MCCC Statistical Office.

#### 16.8 Adverse Event Stopping Rules

Note: Carboplatin and oxaliplatin are not the study drugs of interest. All adverse event attributions should be made to the lipid/placebo infusion, not to carboplatin/oxaliplatin.

16.81 The stopping rules specified below are based on the knowledge available at study development. We note that the Adverse Event Stopping Rule may be adjusted in the event of either (1) the study re-opening to accrual or (2) at any time during the conduct of the trial and in consideration of newly acquired information regarding the adverse event profile of the treatment(s) under investigation. The study team may choose to suspend accrual because of unexpected adverse event profiles that have not crossed the specified rule below.

16.82 Adverse events will be monitored separately by arm; the principal investigator will remain blinded. Accrual will be temporarily suspended to this study if at any time we observe events considered at least possibly related to study treatment (i.e. an adverse event with attribute specified as “possible”, “probable”, or “definite”) that satisfy either of the following:

- if there are 2 or more Grade 3 or higher adverse events at least possibly attributable to lipids in the first 5 patients on the lipid arm.
- if after the first 5 patients on the lipid arm have been treated, there are 40% or more patients with Grade 3 or higher adverse events at least possibly attributable to lipids.
- if any Grade 5 adverse events are observed that are related to study treatment (lipids/placebo).

Note: Historically, lipids have been administered frequently in cancer settings with minimal toxicity. We do not expect any further complications due to the lipids. With that in mind, we maintain a cautious mindset when monitoring these toxicities.

16.83 If accrual is temporarily suspended, the study will be reviewed to determine whether accrual should continue or be permanently closed.

16.84 We note that we will review Grade 4 and 5 adverse events deemed “unrelated” or “unlikely to be related”, to verify their attribution and to monitor the emergence of a previously unrecognized treatment-related adverse event.

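### Section 16.8 rates relatedness to lipid/placebo only, so platinum reactions have no recorded attribution and may count toward the lipid accrual suspension

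*Combined protocol and SAP*

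**What the plan says.** All references are to the combined protocol and SAP.

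- **Attribution.** The note opening section 16.8 reads "All adverse event attributions should be made to the lipid/placebo infusion, not to carboplatin/oxaliplatin". Section 10.3 gives a five-level scale from definite to unrelated. Section 16.84 has Grade 4 and 5 events reviewed when they were judged unrelated or unlikely to be related.
- **Endpoint.** Section 16.11 names "time-to-carboplatin or oxaliplatin acute hypersensitivity reaction", of any grade. Section 16.31 gives "the time to healthcare provider reported hypersensitivity reactions from either carboplatin or oxaliplatin". Section 11.0 asks only "whether a patient developed a healthcare provider-witnessed hypersensitivity reaction or not" and sets no condition on cause.
- **Censoring.** Under section 11.0, patients who stop platinum for a reason other than a hypersensitivity reaction "will be censored on the date of their last study infusion".
- **Off study.** Section 13.4 lists "Treatment related adverse event (immune reaction or unexpected CTCAE" (Grade 3 or higher) among the reasons.
- **Accrual suspension.** The first bullet of section 16.82, which concerns the lipid arm, applies "if there are 2 or more Grade 3 or higher adverse events at least possibly attributable to lipids in the first 5 patients". The second applies after those 5 and is met when 40% or more of patients have such an event. A rating of possible is enough.
- **Overlap of the two roles.** Allergic reaction is a solicited adverse event (10.61). Lipid/placebo runs immediately before platinum (7.1), with bag and tubing masked (6.64). Hypersensitivity is a listed lipid toxicity at under 1% (15.17).

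**The concern.** The same clinical event is both the primary endpoint and a solicited adverse event, and the two systems use different rules about cause. Section 16.31 makes the endpoint causal, 11.0 does not, and 16.8 has relatedness judged against one agent only. Nothing in the plan records whether a reaction was thought to come from platinum. Section 18.5 asks for documentation proving a reaction, but not for its cause or its onset time.

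The exposed part is the suspension rule. A blinded clinician who sees a reaction during platinum, shortly after a masked infusion that can itself cause hypersensitivity, may find it hard to rate below possible. No sentence says whether endpoint reactions are left out of 16.82. The first two triggers look at the lipid arm alone, so residual platinum reactions there could suspend accrual even if placebo patients were reacting more often.

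**Working it through.** **1. The passages side by side.** If the note means that relatedness is rated for lipid/placebo only, a reaction thought to be due to platinum can be entered as unrelated or unlikely, and 16.84 has something to review. On that reading the note is workable, but the word from in 16.31 has no attribution data behind it. If a reaction is rated possible for lipid and is Grade 3 or higher, it counts in 16.82 whether or not platinum caused it.

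**2. Plan inputs.** Section 16.4 gives a hazard ratio of 3.8, a median of about 2 months (taken here as placebo), and 20 patients for 80% power at one-sided 5%. Freedman's formula gives (1.645 + 0.842)² × (4.8/2.8)² = 6.18 × 2.94 = 18.2, so 19 events. With 10 per arm, medians of 2 and 7.6 months and 24 months of follow-up, about 18.9 events are expected. The plan's inputs are therefore used as they stand. The plan gives no operating characteristics for 16.82.

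**3. Lipid-arm reaction risk, two versions.**
- Under 16.4, over the 4 months of treatment expected in 16.5: 1 − 0.5^(4/7.6) = 30.6%. The placebo figure is 1 − 0.5^(4/2) = 75%.
- Under the 30% carboplatin incidence in section 1.2, with the same hazard ratio: 1 − 0.70^(1/3.8) = 9.0%.

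**4. Chance that at least 2 of the first 5 lipid patients have a counted reaction.** P = 1 − (1−p)^5 − 5p(1−p)^4, where p is the risk of a Grade 3+ reaction charged to lipid. The documents give no Grade 3+ share, so it is varied. Every such reaction is assumed to be charged to lipid.

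| Lipid-arm risk | Grade 3+ share | p | P(at least 2 of 5) |
|---|---|---|---|
| 9.0% | half | 4.5% | 1.8% |
| 9.0% | all | 9.0% | 6.7% |
| 30.6% | a quarter | 7.6% | 5.0% |
| 30.6% | half | 15.3% | 17.0% |
| 30.6% | all | 30.6% | 48.3% |

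For comparison, if only true lipid events count, at an assumed Grade 3+ rate of 1% to 5%, the same formula gives 0.1% to 2.3%.

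**5. Adding the second bullet.** With the 40% rule checked after each lipid patient from the 6th to the 20th (simulation, 100,000 runs), the chance of meeting either rule is 9% at p = 10%, 19% at 15% and 59% at 30%. The first five alone give 8%, 16% and 47%.

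**6. Unit of count.** Read literally, the first bullet counts events and the second counts patients. Two Grade 3 terms from one reaction in one patient would meet the first. The figures above count patients, so they leave this route out.

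**The case against.** The strongest reply is that the note names the agent to be rated and does not dictate the answer. Section 10.1 asks whether an event is related to the study intervention, 10.3 allows unrelated, and 16.84 would be empty if every event had to be charged to lipid/placebo. That stands. A reader might infer that 16.8 forces each platinum reaction to be recorded as lipid-related; the documents do not support this.

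A reader might also infer that endpoint reactions can be censored, by joining the off-study reason in 13.4 to the censoring rule in 11.0. They do not support this either. Section 11.0 censors only patients who stop platinum for a reason other than a hypersensitivity reaction, and 16.31 censors at the last infusion with no reaction. Section 7.1 continues study infusions until a witnessed reaction, so an immune reaction in 13.4 may simply be the endpoint being reached. Censoring would need the word from in 16.31 applied strictly and 11.0 set aside.

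It is also fair that one event may properly appear both as an endpoint and as an adverse event, that crossing 16.82 leads to temporary suspension and review (16.83), that the rule may be adjusted (16.81), and that the DSMB reviews safety data (16.7). These points limit the consequence. They do not supply the missing attribution to platinum, and they do not say whether endpoint reactions count in 16.82.

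**Conclusion.** The concern holds as a gap in the rules, not as a contradiction that must corrupt the endpoint. Sections 11.0 and 16.31 differ on whether cause matters, no attribution to platinum is called for, and a Grade 3+ platinum reaction on the lipid arm rated only possible for lipid counts toward suspension.

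If such reactions are counted, the chance of meeting the first trigger is about 2% at a 4.5% risk and 17% at a 15% risk. The 48% figure is an extreme: it needs the 16.4 assumptions, every reaction at Grade 3 or higher, every one charged to lipid, and all five patients observed for 4 months. The Grade 3+ share and the share charged to lipid are both assumptions. Nor does the plan close the trial when a trigger is met; it suspends accrual for review. The events-versus-patients difference between the bullets is real but minor. The change is worth making because it is cheap and removes a suspension route that may have nothing to do with lipid toxicity.

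**What to change.** - Replace the 16.8 note with separate attribution of each event to lipid/placebo and to platinum, and record each reaction's onset time relative to each infusion.
- State in 16.82 that only events judged at least possibly related to lipid/placebo count, and say expressly whether witnessed platinum reactions are included.
- Count patients in both bullets. Two of 5 is already 40%, so the two then agree.
- Reconcile 11.0, 13.4 and 16.31 to one endpoint definition, applied identically in both arms and not dependent on a causal judgement, such as the witnessed reaction in 11.0. Add a sensitivity analysis limited to reactions that start after platinum begins. Requiring platinum causation in the primary endpoint is not advised: only one arm receives lipid, so removing reactions judged due to lipid can act on that arm alone and favour it.

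The cost is one attribution field, one time field and some wording. The small downside is that reactions judged unrelated to lipid drop out of the lipid rule, so review of the kind in 16.84 should continue for them.
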